8.2 Secondary Endpoints and Observation Method

- 1). Duration of response (DoR): defined as the time from the date of first record of objective response (CR or PR) to the first occurrence of progression or death.
- 2). Time to progression (TTP): defined as the time from the date of randomization to any documented radiological tumor progression.
- 3). Disease control rate (DCR): defined as the percentage of subjects with CR, PR and SD (≥ 6 weeks) in the evaluable population.
- 4). Progression-free survival (PFS): defined as the time from randomization to any documented radiological tumor progression or death.
- 5). Overall survival (OS): defined as the time from randomization to death from any cause.

8.3 Independent Tumor Imaging Evaluation

In order to provide objective, neutral and reproducible efficacy data except investigators' evaluation, the 3rd-party Independent Radiology Review Committee (IRC) will be set up for tumor response evaluation in this study.

All the images (including unscheduled scan, possibly including bone scan or brain scan) obtained from each center will be centrally reviewed by IRC, and tumor evaluation will be performed in accordance with RECIST v1.1. The central evaluated data will be used for analysis of ORR, TTP, DoR and DCR. The clinical decisions related with response evaluation will be based on investigator's evaluation.

The detailed procedures and standard for central evaluation will be defined in the additional "Radiology Manual for Study Center".

9. SAFETY EVALUATION

The safety evaluation of investigational drug includes vital signs, laboratory parameters, AE, SAE, treatment-related AE and SAE, which will be evaluated according to NCI-CTC AE v4.03 criteria.

9.1 Adverse Events

9.1.1 Definition of AE

AE is defined as adverse medical event that occurs after the subject who receives a drug in clinical trial, but do not necessarily have a causal relationship with the treatment. Any AE from the signature of informed consent form to 90 days after the last dose will be collected. AE can be any undesirable and unexpected symptom, sign, laboratory abnormal or disease, including at least the following conditions:

- 1) Aggravation of existing (prior to enrollment of clinical trial) medical condition/disease (including exacerbation of symptoms, signs, abnormal laboratories);
- 2) Any new occurrence of AE: any adverse medical condition newly occurs (including symptom, signs, newly diagnosed diseases);
- 3) Abnormal laboratory test or result of clinical significance.

The investigators should carefully record any AE occurs in the subjects, including: description of adverse event and relevant symptoms, time of onset, severity, causality with investigational drug, duration, actions taken, final outcomes and prognosis.

9.1.2 Judgment standard on severity of AE

Refer to NCI-CTC AE v4.03 grading criteria for AE related drugs. If any AE is unlisted in NCI-CTC AE v4.03, refer to the following criteria:

Grade	Clinical description of severity
1	Mild; without clinical symptoms or mild clinical symptoms; only with clinical or laboratory abnormalities; no treatment is required.
2	Moderate, requiring minimal, local or non-invasive treatment; age-appropriate limits activities of daily living (ADL); involving tools refer to cooking, shopping, calls and counting money, etc.
3	Severe conditions or serious medical symptoms but not life-threatening; leading to hospitalization or hospitalization prolonged; leading to disability; limited in self-care ADL. Daily self-care includes bathing, dressing, undressing, eating, going to the bathroom, medication, and so on, non-bedridden.
4	Life-threatening, emergency treatment is required.
5	Leading to death.

9.1.3 Judgment standard on causality assessment

Collection of AE starts from the signing of informed consent form to 90 days after the last dose of investigational drug, records are collected regardless of whether the event is related to the investigational drug, whether the subject is assigned to the experimental arm, or even whether the drug is used or not. Any discomfort or abnormal change in objective laboratory tests during the treatment should be recorded accurately, and the severity, duration, actions taken and outcome of the AE should be recorded. The study doctor should determine the relationship between AE and investigational drug, such as whether the occurrence of AE has relationship with a reasonable medication order, the properties of investigational drug, toxicological and pharmacological effects of investigational drug, subjects' use of other concomitant drugs, subjects' underlying diseases, medical history, family history and provocative and re-provocative reactions, etc. The causality between AE and investigational drug will be assessed using the following 5 categories: "definitely related", "possibly related", "unlikely related", "not related", and "unassessable". Among them, AEs with a causality of "definitely related", "possibly related", "unlikely related" and "unassessable" will be listed as adverse drug reactions.

9.1.4 Follow-up of AE

An AE will be followed up until it is resolved, returns to the baseline level or \leq Grade 1, or reaches a stable state, or until other reasonable time points (e.g., lost to follow-up, death).

9.2 Serious Adverse Event (SAE)

9.2.1 Definition of SAE

Serious adverse events (SAE) is defined as the medical events that require hospitalization or prolonged hospitalization, disability, limiting working ability, life-threatening or death, and leading to congenital malformation during the clinical trial. Including the following medical events:

- Events leading to death;
- Life-threatening events (defined as the subject has a risk of immediate death);
 - Events requiring hospitalization or prolonged hospitalization;
 - Events that result in persistent or severe disability/dysfunction/limiting working ability;
 - Congenital abnormalities or birth defect;
- Other significant medical events (defined as the event threatens the safety of the subject, or requires intervention measures for the prevention of any of the above conditions).

9.2.2 Disease progression

Disease progression is defined as the exacerbation of the subject caused by indications of the investigational drug, including radiological progression and progression of clinical symptom and sign. New metastases relative to the primary tumor and the progression of the original metastases are both considered to be progressive disease. Events that are life-threatening, requiring initial or prolonged hospitalization due to symptoms and signs of disease progression, which can lead to permanent or severe disability/dysfunction/limiting work ability, congenital abnormalities or birth defects are not reported as SAEs in expedition. Death caused by symptoms and signs of disease progression is reported as SAE.

9.2.3 Hepatic enzyme abnormalities

Hepatic enzyme abnormalities with abnormal values in AST and/or ALT and meet the laboratory abnormalities in the following table should be reported as SAE. Additional follow-up of subjects will be required until the hepatic enzyme returns to the baseline level.

Baseline period	Normal (AST, ALT, and TBIL)		Abnormal (AST, ALT, or TBIL, any of them)	
Treatment period	ALT $\geq 3 \times$ ULN	AST $\geq 3 \times$ ULN	ALT $\geq 8 \times$ ULN	AST $\geq 8 \times$ ULN
	Meeting one of the above two criteria, with TBIL $\geq 2 \times$ ULN and alkaline phosphatase $\leq 2 \times$ ULN with no hemolysis		Meeting one of the above two criteria, with TBIL $\geq 3 \times$ ULN or increase $\geq 1 \times$ baseline value	

9.2.4 Other anti-cancer therapy

The record of AE starts from the signing of informed consent form until 90 days after the last dose of investigational drug. SAEs occurring within 90 days after the last dose also need to be reported even if the subject has started to use other anti-cancer drugs.

9.2.5 Hospitalization

AEs that result in hospitalization or prolonged hospitalization should be considered as SAEs. Any initial hospitalization meets the criteria.

Hospitalization does not include the following situations:

- Rehabilitation facilities
- Nursing homes
- Routine emergency room admissions
- Surgeries at the same day (as outpatient/same day/ambulatory procedures)

Hospitalization or prolongation of hospitalization which are unrelated to the exacerbation of AEs will not be considered as SAEs. For example,

- Admission for treatment of a preexisting condition without the development of new adverse events or worsening of the preexisting condition (e.g., for check of persistent pre-trial laboratory test abnormality);
- Administrative admission (e.g., for yearly physical exam);
- Hospitalization as per the trial protocol during the study (e.g., as required by the protocol);
- Elective admission not associated with the aggravation of adverse events (e.g., elective surgery);
- Predefined treatments or surgical procedures should be documented throughout the study program and/or in the baseline data of individual subject.

- A subject is hospitalized due to only use of blood products.

Diagnostic or therapeutic invasive (e.g., operation) and non-invasive procedures should not be reported as AE, but if the disease condition leading to the operation, it should be reported as long as it conforms to the definition of AE, e.g., acute appendicitis during the AE reporting period should be reported as AE; therefore, the appendectomy should be recorded as the treatment of AE.

9.2.6 Reporting procedures of SAE

The reporting of SAEs starts from the signing of informed consent form to 90 days (inclusive the 90th day) after the last dose of investigational drug. In case of SAE, regardless of first report or follow-up report, the investigators must fill in the “serious adverse event report form” immediately, sign and date it, report it to the sponsor within 24 hours after learning of it, and report it to relevant organizations in time as required by regulations.

The sponsor’s email to receive SAE report in this study: [contact]

The SAEs occurring 90 days after the last dose of investigational drug will generally not be reported, unless it is suspected to be related to the investigational drug. The detailed record content of SAE should include symptoms, severity, and causality with investigational drug, time of onset, time of treatment, actions taken, follow-up time and method as well as outcome. If the investigator considers that an SAE is not related to investigational drug while potentially related to the study conditions (e.g., termination of the original treatment or complications during the trial), the relationship should be described in detail in the narrative section of SAE report form.

If there is a change in the severity of an ongoing serious adverse event or its relationship with the investigational drug, follow-up reports should be submitted immediately. If misinformation is considered to be present in the previously reported SAE, it can be corrected, withdraw or degraded in the follow-up report, and reported in accordance with the SAE reporting procedure.

9.2.7 Follow-up of SAE

An SAE should be followed up until it is resolved, returns to the baseline level \leq Grade 1, or reaches a stable state, or until other reasonable time points (e.g., lost to follow-up, death).

9.3 Pregnancy

If a female subject is pregnant during the clinical study, the subject will be withdrawn from the group, investigators should fill in “Pregnancy Report/Follow-up Form in Hengrui Clinical Study”, and report to the sponsor within 24 hours after investigator awareness.

If the partner of male subject becomes pregnant during the clinical study, the subject can continue the clinical trial, investigators should fill in “Pregnancy Report/Follow-up Form in Hengrui Clinical Study”, and report to the sponsor within 24 hours after investigator awareness.

The investigator should follow up the pregnancy result, until one month after delivery, and will report the result to sponsor.

If the outcome of pregnancy is stillbirth, spontaneous abortion, or fetal malformations, it should be considered as an SAE and be reported in accordance with SAE reporting requirements.

If an SAE occurs during pregnancy, the investigator is required to complete the “Serious Adverse Event Report Form” and report this SAE according to the reporting procedures.

9.4 AEs of Special Interest

For the AE of special interest specified in the clinical study protocol, investigators need to fill in the “Adverse Event of Special Interest Report Form in Hengrui Clinical Study” within 24 hours after awareness, and report to the sponsor.

If it is SAE at the same time, please also fill in “Serious Adverse Event Report Form” and report to the relevant department in accordance with SAE procedure.

- \geq Grade 3 infusion reaction
- \geq Grade 2 diarrhea/colitis, uveitis, or interstitial pneumonia
- \geq Grade 3 other immune-associated adverse events
- Any possible event of abnormal hepatic enzyme (see Section 9.2.3, whilst lacking other related causes, for example, progression of disease, acute viral hepatitis, cholestasis, concomitant medication, pre-existing hepatopathy, etc.)
- Grade 4 increased amylase or lipase

9.5 Emergency Unblinding

Not applicable.

10 DATA MANAGEMENT

10.1 Material Collection and Data Management

Electronic case report form (eCRF) will be used for collection and management of the study data in this study.

10.1.1 Collection of data

eCRF is used for acquisition of study data in this study; the electronic data collection (EDC) system will be provided by Jiangsu Hengrui Pharmaceuticals Co., Ltd. to study institutions. The company’s staff will train on EDC system for the designated personnel at the study institutions. The personnel at the study institutions can login EDC system only after the training. PI or specialized person for data entry (qualified investigator and/or CRC) should enter the data into

EDC system in accordance with the requirement for visit procedure and the guideline on filling in eCRF. The system logic verification program will check the completeness and logicity of the clinical trial data entered in EDC system, and generate error message for the problem data, allowing PI, investigator or CRC to modify or explain the data. After the database is locked, investigators will receive one CD-ROM or hard copy of the data, for archival at the study institution.

10.1.2 Data management and quality control

In order to ensure the clinical data are true and reliable, improve the quality of clinical data, clinical monitors will review the completeness, consistency and accuracy of the trial data in clinical database in accordance with monitoring plan during the trial, and discuss with the study staff on the problem data, and the study staff should make supplement or correction when necessary. The clinical monitor or data management professionals will propose their queries on the questionable data to PI, investigator or CRC in a form of electronic query table, PI, investigator or CRC must respond to the queries and make correction or explanation to the problem data, the query can be proposed for multiple times until the problem data are solved, if necessary. The person in charge of medical affairs, drug safety affairs and data management professionals will conduct consistency comparison for SAE on a regular basis.

At the end of the trial, the data management professionals and medical staff will do the final quality control of all the data in the database, summarize all the protocol deviations and violations appeared in the trial, and convene data verification meeting. After the data in the database meet the requirement for quality, the database will be locked, the data management professionals will export data for analysis by statistical department.

10.1.3 Data review and monitoring of study institution

At the initiation of the trial, the representatives from Jiangsu Hengrui Pharmaceuticals Co., Ltd. will introduce the protocol and eCRF together with investigators and working staff at the first visit to study institutions or in the investigator's meeting. During the trial, the monitor will visit study centers on a regular basis, check the completeness of record and accuracy of the content on eCRF, compliance with the protocol and Good Clinical Practice, progress in enrollment, and make sure the investigational drug is stored, dispensed and counted in accordance with the provisions. During these visits, the key study staff must be able to assist the monitors.

Investigators must keep the original documents of each subject participating in the trial, including the study medical records and visit records (hospitalization or outpatient medical record), which include demographic parameters and medical information, laboratory data, ECG and results of any other examination or evaluation. All the information on eCRF must be sourced from the original document in the subject's archives. Investigators also have to keep the informed consent forms signed by subjects.

Investigators must confirm all the relevant original documents can be monitored, so as to verify the consistency with that on eCRF. The monitoring standard by Jiangsu Hengrui Pharmaceuticals Co., Ltd. requires a 100% monitoring for study-related original documents, including but not limited to informed consent form signed by the subject, compliance with inclusion/exclusion criteria, visit record, AE/SAE record, and all the data required for evaluation of the main efficacy and safety parameters. Any information on subject's identity in the original documents will not be disclosed.

11 DATA ANALYSIS AND STATISTICAL METHODS

The detailed summary of the data collected in this study and the statistical analysis method will be recorded in the statistical analysis plan (SAP), and will be finalized and put on record by the sponsor. If any change to the study protocol is judged by the sponsor or the principal investigator to have an impact on the statistical analysis plan, the SAP needed to be re-modified so as to keep consistency with the study protocol.

11.1 Determination of Sample Size

This is a single-arm, open-label phase II study to observe the objective response rate (ORR) and survival rate at 6 months simultaneously.

Referring to the study results on similar products, assuming the ORR is 15% for SHR-1210 in treatment of target population of this study, and the lower limit of 95% confidential interval of ORR obtained from this study is >7%, it can be considered as effective. 154 subjects need to be enrolled to obtain 90% power at a one-sided significance level of 0.025. Further assuming evaluable cases accounting for 80% of the enrolled subjects, 194 subjects are required to be enrolled.

Assuming the survival rate at 6 months is 80% for SHR-1210 in treatment of target population, and the lower limit of 95% confidential interval is >70%, this therapy can be considered to have advantage in efficacy. 200 subjects need to be enrolled to obtain 90% power at a one-sided significance level of 0.025. Considering the drop-out rate of 10%, a total of 220 subjects are required to be enrolled.

Therefore, the planned sample size of this study is 220.

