8 EFFICACY EVALUATION

8.1 Primary Endpoints and Observation Method

- 1) 6-month survival rate (6-month OS%): defined as the percentage of non-death cases in the evaluable subjects from the start of the trial to 6 months.
- 2) Objective response rate (ORR):

Defined as objective tumor response evaluated based on RECIST v1.1, including CR and PR cases.

Definition of evaluable population: all the subjects meeting the following criteria, i.e., having received at least one dose of SHR-1210 treatment and at least one tumor evaluation after the start of study treatment. If the efficacy reaches CR or PR, subjects must receive repeated test for confirmation in no less than 4 weeks (28 days) after the first evaluation.

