11.2 Analysis Populations

Full analysis set (FAS): an analysis set determined in accordance with intention-to-treat principle. All the subjects who are randomized and have documented at least one dose of investigational drug will be included in this analysis set. The full analysis set is the primary efficacy analysis set.

Per protocol set (PPS): one subset of full analysis set. The subjects with protocol violation which has important influence on efficacy will be excluded from this set. The list of subjects who are included or excluded from PPS needs to be determined through review by the sponsor and investigators prior to lock of database.

Safety analysis set (SS): all the subjects who are randomized and have documented at least one dose of investigational drug will be included in the safety analysis set.

PD-L1 analysis set: PD-L1 expression analysis set of this trial comprise of all the subjects who have been randomized and enrolled and have received at least one dose of the investigational drug, and have provided tumor biopsy samples.

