11.3.2 Efficacy analysis

The tumor evaluation will be performed by the investigators based on RECIST v1.1. This evaluation data will be based on following responding parameters: complete response (CR), partial response (PR), stable disease (SD), progression of disease (PD), and not evaluable (NE). All the efficacy analysis will be based on the full-analysis set.

The survival distribution of OS will be estimated based on Kaplan-Meier (KM) method, median OS and two-sided 95% confidential interval will be calculated. In addition, KM method will be used to estimate the probability of survival at different time points (at month 6/9/12), and the corresponding 95% confidential interval will be calculated. Moreover, the subgroup analysis of OS will be performed by the predefined factors, the analytical method will be based on the aforementioned method.

The survival distribution of time to progression (TTP) will be estimated based on Kaplan-Meier (KM) method, median TTP and two-sided 95% confidential interval will be calculated.

The survival distribution of progression-free survival (PFS) will be estimated based on Kaplan-Meier (KM) method, median PFS and two-sided 95% confidential interval will be calculated. Objective response rate (ORR) and disease control rate (DCR): Clopper-Pearson method will be used to calculate the 95% confidential interval of overall percentage.

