3. STATISTICAL HYPOTHESIS

All analyses will be primarily based on descriptive statistical summary by group and overall. No formal statistical hypothesis testing will be performed. The overall 95% CIs of the two primary study endpoints, ORR and 6-month OS rate, will be calculated. The lower limit of the overall 95% CI of ORR is > 7% and the lower limit of the overall 95% CI of 6-month OS rate is >70% indicate that the drug is effective.

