5. STATISTICAL ANALYSIS

5.1. General Considerations

5.1.1. Analysis sets

Full analysis set (FAS)

Full analysis set includes all the randomized subjects who have received at least one dose of the investigational drug. Based on the analysis in the FAS, subjects belong to their allocated group as randomized rather than the actual medication group.

Per-protocol set (PPS)

It is a subset of the FAS. The PPS forms by excluding subjects with protocol deviation that has important effect on the study results from the FAS. Analysis based on the PPS, as supportive analysis, will be used as a supplement to the analysis based on the FAS. The PPS must be determined by the medical team and the statistical team of the project prior to database lock for the final analysis. All protocol deviations, including those that are judged to have major effect on the study results, will be presented in study report in a form of listing.

Evaluable set (ES)

Evaluable set is also a subset of the FAS and defined as the subjects with at least one post-baseline tumor evaluation in the FAS.

Safety set (SS)

Safety set includes all the subjects who have received at least one dose of the investigational drug. Based on the analysis in SS, subjects belong to the actual medication group (as treated). The safety set is the primary set for the safety analyses.

PD-L1 set (PD-L1)

PD-L1 set of this study comprises of all subjects who have been randomized and have received at least one dose of the investigational drug, and have provided tumor biopsy samples.

Table 1. Correspondence between study endpoints and analysis sets

Endpoints	Analysis Sets				
	FAS	PPS	ES	SS	PD-L1
ORR (%)	X	X	X		X
6/9/12-month OS rate (%)	X	X			X
TTP (months)	X				
PFS (months)	X				
DoR (months)	X				
DCR (%)	X	X	X		
OS (months)	X				
TTR (months)	X				
Safety (AE, LAB, VS, ECG, PE)				X	

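### The 90% power for ORR is calculated for evaluable subjects, but the primary analysis set is the FAS, for which no ORR power is stated

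*Protocol*

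**What the plan says.** Protocol 11.1, repeated in the synopsis and in SAP 2.3, sizes ORR by "assuming the ORR is 15% for SHR-1210 in treatment of target population of this study" and requiring the lower 95% confidence limit to exceed 7%. It obtains 154 subjects for 90% power at one-sided 0.025, and continues: "Further assuming evaluable cases accounting for 80% of the enrolled subjects, 194 subjects are required to be enrolled". The planned total of 220 comes from the separate 6-month OS calculation.

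On analysis sets:

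- Protocol 11.2: "The full analysis set is the primary efficacy analysis set". Membership needs randomization and one dose.
- Protocol 11.3.2: "All the efficacy analysis will be based on the full-analysis set".
- Protocol 8.1 defines evaluable subjects as those "having received at least one dose of SHR-1210 treatment and at least one tumor evaluation after the start of study treatment". Protocol 8.2 takes DCR "in the evaluable population".
- SAP 5.1.1: "Evaluable set is also a subset of the FAS and defined as the subjects with at least one post-baseline tumor evaluation in the FAS".
- SAP 3 gives the criterion for effectiveness, "The lower limit of the overall 95% CI of ORR is > 7" (per cent), without naming a set. SAP 5.4 calculates ORR on the FAS, the PPS and the ES.

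**The concern.** Dividing 154 by 0.8 is needed only if the 154 are evaluable subjects. A dosed subject with no post-baseline scan is outside that count but inside the FAS, and cannot be a confirmed responder. The sizing and the primary analysis therefore use different denominators.

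Two things are at stake. First, the plan states a power for one analysis and names another as primary, so a reader may take 90% as the chance of success on the primary ORR analysis when it could be well below that. Second, the effectiveness rule in SAP 3 can be met on one of the calculated sets and missed on another, and SAP 3 does not say which one decides.

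**Working it through.** **Inputs.** Assumed ORR 15%, threshold 7%, one-sided 0.025, 90% power, n = 154, 80% evaluable, 194, total 220 (Protocol 11.1). Clopper-Pearson interval (Protocol 11.3.2, SAP 5.4). FAS = randomized and dosed (Protocol 11.2, SAP 5.1.1).

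**Method.** For x responders out of n, the lower limit L(x, n) is the 2.5% quantile of Beta(x, n − x + 1). Let r be the smallest x with L > 7%. Power is P(X ≥ r) for X ~ Binomial(n, p).

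**1. The plan's own figure.** For n = 154, r = 18, the one-sided error at 7% is 0.0227 and power at 15% is 90.0%. At n = 153 power is still below 90%, at 0.8945, and 154 is the smallest n that reaches it. The plan's 154 is reproduced. The inflation is 154 / 0.8 = 192.5, so 193 against the stated 194, a trivial difference.

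**2. Moving to the FAS.** Of 220 enrolled, 220 × 0.80 = 176 are evaluable and 44 are not. If the 15% is per evaluable subject and all 44 are dosed, the FAS rate is 176 × 0.15 / 220 = 12%. This product is mine; it is not in the documents. If some of the 44 are never dosed, they leave the FAS and its rate rises, for example 26.4 / 198 = 13.3% with 22 undosed.

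**3. Exact FAS power at 220 enrolled.**

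| Assumption | FAS n | FAS rate | r | Power |
|---|---|---|---|---|
| 15% per evaluable, 80% evaluable, all dosed | 220 | 12.0% | 24 | 72.1% |
| same, 85% evaluable | 220 | 12.75% | 24 | 82.0% |
| same, 90% evaluable | 220 | 13.5% | 24 | 89.2% |
| same, 90.7% evaluable | 220 | 13.6% | 24 | 90.0% |
| 80% evaluable, 11 of the 44 undosed | 209 | 12.6% | 23 | 78.9% |
| 80% evaluable, 22 of the 44 undosed | 198 | 13.3% | 22 | 84.8% |
| 80% evaluable, all 44 undosed | 176 | 15.0% | 20 | 93.2% |
| 15% per dosed subject | 220 | 15.0% | 24 | 96.8% |

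For comparison, the evaluable-set analysis (n = 176, 15%, r = 20) has power 93.2%.

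**4. Where the sets disagree.** Take 220 dosed and 176 evaluable. The rule needs 20/176 (lower limit 7.08%) on the evaluable set and 24/220 (7.12%) on the FAS; 23/220 gives 6.74% and fails. So 20 to 23 responders pass on the evaluable set and fail on the FAS. With 176 evaluable at 15%, P(20 ≤ X ≤ 23) = 20.7%.

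**5. False-positive risk.** At a true rate of 7%, P(X ≥ 24 | n = 220) = 0.021, so the FAS analysis does not exceed 0.025.

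**The case against.** The best case against has five parts.

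- **The 72% is conditional.** Among the readings that keep the plan's 80%, it is the lowest. The only words attached to the 15% refer to the target population, which does not mean evaluable subjects. On that wording FAS power is 96.8% and the 0.8 step is only padding. This stands as a reason to quote the range. It does not remove the inconsistency: if the 15% is per dosed subject, the inflation serves no purpose and the text still needs correcting.
- **The 80% is a share of enrolled subjects.** The documents do not split the non-evaluable into dosed and undosed. This is correct, and the table shows the effect.
- **Little depends on it.** 6-month OS sets the 220, no ORR power is claimed at 220 for any set, and SAP 3 plans no formal testing. With SAP 3.0 dated 16 Sep 2018 and the primary analysis expected by May 2018, a revised sentence would probably not inform enrolment. All fair. But SAP 3 still sets a rule for calling the drug effective, and the protocol attaches 90% power to it.
- **The rule already has a set.** If the FAS is clearly primary, passing on the evaluable set and failing on the FAS is a failure. That is the right reading of Protocol 11.2, but SAP 3 does not say so, and SAP 5.4 calculates ORR on three sets without labelling the evaluable set as supportive.
- **The sharper conflict is in Protocol 8.1.** It defines the evaluable population under the primary endpoints and uses evaluable subjects for 6-month OS. If 8.1 governed ORR, the sizing would match. For ORR, though, 11.2 and 11.3.2 state the primary set expressly. Aligning 8.1 and 8.2 is a sensible addition to the fix.

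**Conclusion.** The concern holds. The 154 and its 90% are correct for an analysis of evaluable subjects; the plan gives no ORR power for the FAS analysis it calls primary. With 220 enrolled and the plan's 80% evaluable, FAS power is 72.1% if the 15% is per evaluable subject and everyone is dosed, and rises to 93.2% as the 44 non-evaluable subjects become undosed. If the 15% is per dosed subject it is 96.8%. On the per-evaluable reading with all subjects dosed, 90% requires about 91% to be evaluable. The number to enrol and the threshold are unaffected, and false-positive risk on the FAS is not inflated. This should be fixed, because it concerns the stated power and the success rule of a primary endpoint.

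**What to change.** 1. In Protocol 11.1, the synopsis and SAP 2.3, label the 154/194 calculation as applying to the evaluable set, state the denominator of the 15%, and add the matching sentence:
   - If per evaluable subject: *Assuming 15% of evaluable subjects respond, 80% are evaluable and all enrolled subjects are dosed, the FAS rate is 12% and 220 subjects give about 72% power for the primary FAS analysis.*
   - If per dosed subject: *Assuming 15% of all dosed subjects respond, 220 subjects give about 97% power for the primary FAS analysis.*
2. In SAP 3, add: *The >7% rule is applied to the IRC-assessed ORR in the FAS; the PPS and ES are supportive.*
3. Optional: carry the SAP 4.1.3 statement that non-evaluable subjects stay in the denominator over to SAP 4.1.1, and align the evaluable-population wording in Protocol 8.1 and 8.2 with 11.2 and 11.3.2.

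The cost is a few sentences. No patients are added, and the primary set and threshold do not change. The downside is that the stated ORR power may look less favourable.
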